8.4.2. EFFECTIVENESS ENDPOINT

Descriptive statistics will be used to describe the effectiveness measures.

8.4.3. TOTAL ENROLLMENT AND FOLLOW-UP

At least 273 enrolled subjects will be inserted with Sensors to achieve at least 1400 Sensor cycles. Subjects will be encouraged to remain in the study up to 27 months of follow-up or after at least 1400 Sensor cycles are completed study wide.

9. OTHER ETHICAL AND REGULATORY CONSIDERATIONS

9.1. STATEMENT OF COMPLIANCE AND GOOD CLINICAL PRACTICE

This clinical investigation will be conducted in compliance with the principles that have their origin in the Declaration of Helsinki (Revision 6, 2008), this clinical investigation plan, requirements of the approving IRB, US Code of Federal Regulations applicable to clinical studies, ICH GCP E6, ISO 14155 and other applicable regulatory requirements. This clinical investigation

Confidential Information

Senseonics, Inc.

Page 40 of 43 Effective Date:#: 20 March

Protocol #: CTP-0034, Version 10

will not be initiated until approval has been obtained from the FDA as well as respective internal review boards. No deviation from the protocol will be implemented without the prior review and approval of sponsor and/ or IRB except where it may be necessary to eliminate an immediate hazard to a subject.

9.2. INFORMED CONSENT AND INTERNAL REVIEW BOARD

The Investigator is responsible for assuring that informed consent is obtained from each subject or (legally authorized representative) prior to participation in the clinical investigation, according to the local clinical site's IRB and applicable regulatory requirements.

The Investigator will prepare an informed consent form (ICF) in accordance with this protocol and applicable regulatory requirements. Prior to the start of the study or revision to study, the informed consent form will be reviewed by the Sponsor for consistency with protocol, and then must be submitted to and approved by the IRB. A copy of the final IRB approved consent form and notification of approval of the clinical protocol must be received and approved by the Sponsor prior to start of study or revision to study. Timely approvals for the continuation of the trial as well as the informed consent form at each clinical site must also be forwarded to the Sponsor.

While an Investigator may discuss general availability of the investigation with a prospective subject without first obtaining consent, informed consent must be obtained from a subject prior to initiation of any clinical procedures dictated by the protocol (e.g., pregnancy testing) that are performed solely for the purpose of determining eligibility to participate in the clinical investigation.

The informed consent process includes both verbal and written explanation. Subjects must be fully counseled and informed of their options, risks and benefits, and have every opportunity to ask questions about participation in the investigation. This process includes a thorough explanation of the informed consent document that the subject will be asked to sign acknowledging that they understand and desire to participate in the investigation. The subject will be provided a copy of the signed informed consent form. The original ICF remains at the investigational site.

If new information regarding the device becomes available and/or the protocol changes and this information can significantly affect a subject's future health and medical care, subjects will be informed of the information and may be asked to sign a revised informed consent form.

The Investigator will notify the Sponsor within 5 working days, a withdrawal of approval by the reviewing IRB of the investigator's part of an investigation.

9.3. SUSPENSION OR PREMATURE TERMINATION OF CLINICAL INVESTIGATION

Senseonics, Inc. Confidential Information Page 41 of 43
Protocol #: CTP-0034, Version 10 Effective Date:#: 20 March

The study may only be terminated prematurely for safety reasons.

9.4. AMENDMENTS TO THE PAS PLAN

Investigators may not modify this protocol without obtaining written concurrence of the Sponsor and approval by the IRB and required regulatory authorities.

9.5. DEVICE ACCOUNTABILITY

The Eversense CGM System will be used in accordance with its approved product labeling. The treating HCP will follow applicable hospital (institutional) guidelines. The HCP shall maintain complete records of the date of implantation, subject identification and follow applicable hospital guidelines in relation to traceability of implantable devices.

9.6. INTERIM REPORTING REQUIREMENTS TO FDA

In order to allow HCPs and patients to make informed health care decisions while this post-approval study is being implemented, information about this ongoing study will be provided to the US FDA on an ongoing basis including:

- Number of study sites enrolled (to be updated after submission of each interim report)
- Number of patients enrolled (to be updated after submission of each interim report)
- Interim summary data on study endpoints.

Information will be provided every 6 months during the first two years of the study and then annually thereafter.

10. STUDY ENROLLMENT, FOLLOW-UP AND COMPLETION MILESTONES

The PAS is expected to meet the following enrollment, follow-up and completion milestones:

- expected monthly number of study sites with IRB approvals
 - 4 sites per month up to 30 sites
- expected date of initiation of subject enrollment
 - o first quarter 2019
- expected number of subjects enrolled per month
 - 15 subjects total per month
- expected date for subject enrollment completion
 - within 36 months of first subject enrollment
- expected date to complete follow-up of all study participants

Senseonics, Inc. Confidential Information Page 42 of 43
Protocol #: CTP-0034, Version 10 Effective Date:#: 20 March

60 months from first enrollment

Enrollment of subjects will not be competitive, as the goal will be to spread the subject total across the clinical sites. It is not expected that each site will enroll the same number of subjects, as the ability to recruit appropriate subjects will vary from site to site.

Subjects will be encouraged to remain in the study for up to 27 months of follow-up or after at least 1400 sensor cycles are completed study wide through the recruitment of subjects with a genuine interest in using new technology to improve the control of their diabetes, and by providing financial assistance to subjects whose insurance may not cover the Eversense CGM System.

The data collected will be analyzed and interim reports will be submitted every 6 months post PAS approval for the first two years and annually thereafter.

It is expected that follow-up for all study subjects will be complete up to 27 months or after at least 1400 sensor cycles are completed study wide after study enrollment is complete (60 months after PAS approval). The final study report will be available approximately 6 months after final subject follow-up.

¹ Rewers M, Pihoker C, Donaghue K, Hanas R, Swift P, Klingensmith GJ. Assessment and monitoring of glycemic control in children and adolescents with diabetes. Pediatr Diabetes. 2009 Sep;10 Suppl 12:71-81.

Senseonics, Inc. Protocol #: CTP-0034, Version 10

5.10	Interim Analyses	11
5.11	Protocol Deviations	11
6	Changes from Planned Analyses	11
7	Subject Listings	11

Statistical Analysis Plan		Page 5 of 11
Sponsor	Study	Version
Senseonics	A Post Approval Study to Evaluate the Long-term Safety and Effectiveness of the Eversense® Continuous Glucose Monitoring (CGM) System	1.0

1 Introduction

This statistical analysis plan (SAP) describes the planned statistical methods to be used during the reporting and analysis of data collected under the Clinical Investigation Protocol CTP-0034. This SAP should be read in conjunction with the study clinical investigation plan (CIP) and case report forms (CRFs). This version of the SAP has been developed with respect to the Clinical Investigation Protocol Version 10, 20 March 2023. Any revisions to the protocol or CRFs that impact the planned analyses may require updates to the SAP.

2 Study Objectives

2.1 Primary Objective

The primary safety objective of the study is to demonstrate the long-term safety of the Eversense CGM System.

The primary effectiveness objective of the study to demonstrate the long-term effectiveness of the Eversense CGM System.

2.2 Study Endpoints

The primary safety endpoint is incidence of the composite of infection, secondary procedures to remove the Sensor, or procedure-related adverse events of at least moderate severity.

The primary effectiveness endpoint is time in range, defined as glucose values between 70 mg/dL and 180 mg/dL, at 12 months compared to the first month post-first Sensor insertion.

3 Study Design

Prospective, multi-center study at up to 30 sites in the U.S. enrolling up to 400 adult subjects with diabetes (to insert 273 subjects) including at least 40 subjects ≥ 65 years to achieve at least 1400 Sensor cycles. The subjects will have one Sensor inserted by trained health care professionals approximately every 3 to 6 months dependent upon the Sensor used (90-day Eversense Sensor or 180-day Eversense E3 Sensor).

3.1 Blinding

There is no blinding in this study.

Statistical Analysis Plan		Page 6 of 11
Sponsor	Study	Version
Senseonics	A Post Approval Study to Evaluate the Long-term Safety and Effectiveness of the Eversense® Continuous Glucose Monitoring (CGM) System	1.0

4 Sample Size Determination

At least 273 enrolled subjects will be inserted with Sensors to achieve at least 1400 Sensor cycles. Subjects will be encouraged to remain in the study up to 27 months of follow-up or after at least 1400 Sensor cycles are completed study wide.

Based on data from the PRECISE (n=81 subjects), PRECISE II (n=90 subjects), PRECISION (n=35 subjects) and PMCF (n=1686 subjects) studies, a total of 31 events occurred that would meet the definition of the primary safety endpoint in this study. With a total of 1892 subjects, this equates to an observed rate of approximately 1.6% with an associated 95% confidence interval of 1.1% to 2.3%. As there is variability associated with this sample, as evidenced by the confidence interval, a conservative expected rate of events for this study is 2.3%. The planned sample size of 1400 total cycles) with this expected rate should provide greater than 95% power for the test of the performance goal of 4%.

Meeting the performance goal of 4% for the planned sample size would require a worst-case observation of a rate of approximately 3% or less (i.e., 41 or fewer events among 1400 cycles). This result will be clinically acceptable and similar to results observed in past studies.

5 Statistical Analyses

5.1 General Considerations

Except where otherwise specified, the following general principles apply to the planned statistical analyses. All statistical analysis will be conducted using SAS version 9.4 or later (SAS Institute Inc., Cary, NC) or other widely-accepted statistical or graphical software as required.

5.1.1 Descriptive Statistics

Continuous data will be summarized with mean, standard deviation, median, minimum, maximum, and number of evaluable observations. Categorical variables will be summarized with frequency counts and percentages. Confidence intervals may be presented, where appropriate, using the t-distribution for continuous data and Clopper-Pearson Exact method for categorical variables.

5.1.2 Study Day

Study day 0 is the date of the index procedure. Day in study will be calculated relative to the index procedure as follows:

$$\text{Study Day} = \text{Assessment Date} - \text{Index Procedure Date}$$

For each subject, duration in study will be based on last study contact date which is the latest date of all follow-up visits, assessments, adverse event onset or resolution, and study exit including date of death.

Statistical Analysis Plan		Page 7 of 11
Sponsor	Study	Version
Senseonics	A Post Approval Study to Evaluate the Long-term Safety and Effectiveness of the Eversense® Continuous Glucose Monitoring (CGM) System	1.0

Duration variables will be calculated as follows:

$$\text{Duration Days} = \text{End Date} - \text{Start Date}$$

5.1.3 Visit Windows

Unless otherwise specified, visit based assessments will be analyzed for each analysis time point according to the nominal visit entered in the Case Report Form (CRF) regardless of if it is out of window.

5.2 Analysis Populations

Primary Analysis population: The primary safety and effectiveness analyses will be based on data from all enrolled subjects in this post approval study (ITT, Intention-to-treat).

Per-Protocol Safety Analysis Population: A per-protocol (PP) population will be identified based on those subjects who met the original inclusion and exclusion criteria, have demonstrated substantial compliance with the protocol and no significant protocol deviations affecting the primary endpoints. Supportive analyses for the primary effectiveness endpoint and all secondary and exploratory analyses will be performed in the PP population.

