8.3. OTHER ENDPOINTS

Safety

Other safety endpoints will be summarized using descriptive statistics appropriate to the endpoint being evaluated. There are no formal hypotheses or tests for statistical significance associated with secondary endpoints.

The rates for serious and non-serious adverse events will be summarized as binomial proportions, together with the exact, one-sided upper 95% confidence bound. These will include insertion/removal procedure-related adverse events, and rate of device breakage.

Subgroup analysis of all safety endpoints based on:

- Age (<65 years vs. >65 years, minimum 40 subjects)
- Diabetes type (I vs. II)
- Race (non-Caucasian vs. Caucasian)

Effectiveness

Effectiveness will be measured as percentage change in the percent time in range (based on hours) at one month compared to 12 months using a time in range definition of glucose values between 70 mg/dL and 180 mg/dL. The Time in Range will be summarized as the mean of the subject percentages, together with the median, standard deviation, minimum, maximum, and 25th / 75th percentiles.

Summary statistics will also be provided for the change in HbA1c levels from baseline, and average hours of use per day.

Patient Perspective

Patient satisfaction as measured by validated questionnaires (CGM satisfaction survey and Diabetes Distress Scale) administered at select visits will be reported. The patient questionnaire scores will be summarized as means, median, standard deviation, minimum, maximum, and 25th / 75th percentiles.

Page 39 of 43

Effective Date:#: 20 March

Other Endpoints

Success rates for insertion and removal procedures will be presented to evaluate the

Senseonics, Inc. Confidential Information Protocol #: CTP-0034, Version 10

effectiveness of the training program. Success rate will also be presented based on the HCP experience with insertion and removing Sensors (learning curve by number of cases). It is anticipated that approximately 30% of the insertion and removal procedures will be done by nurse practitioners and physician assistants.

The rates of serious adverse events based on HCP experience with inserting and removing Sensors (learning curve by number of cases) will be examined.

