5.6.1.1 Primary Analysis

The primary safety composite endpoint will be evaluated in the following hypothesis, against a Performance Goal of 4%:

H0: The rate of the composite of infection, secondary procedures to remove the Sensor, or procedure-related adverse events of at least moderate severity (p) is greater than or equal to 4%.

$$H0: p \geq 4\%$$

H1: The rate of the composite of infection, secondary procedures to remove the Sensor, or procedure-related adverse events of at least moderate severity (p) is less than 4%.

$$H1: p < 4\%$$

The rate will be tested against the Performance Goal of 4%, using an exact, binomial test, with a one-sided p-value of 0.05 considered evidence of statistical significance. For the primary analysis, data will be analyzed on a per cycle basis, with each cycle contributing an independent observation.

The endpoint will be evaluated using the ITT analysis set.

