5.6.3 Additional Safety Endpoints

There are no formal hypotheses or tests for statistical significance associated with additional safety endpoints. Analyses will be based on the general methods outlined in this SAP. The following additional endpoints will be summarized with descriptive statistics, overall, and by subgroups as defined in Section 6.9:

- Rate of all device-related and insertion and removal procedure-related adverse events
- Rate of device breakage
- Rate of device-related and insertion and removal procedure related
- Serious adverse events up to 27 months post-first sensor insertion

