5.8 Safety Analyses

Adverse events (AE) will be reported for the ITT primary analysis population. AEs will be tabulated with the number of events and subjects with event for each event type and overall. Rates will be reported as the number of subjects who experience at least one event during the analysis interval out of the total number of subjects with follow-up to the beginning of the analysis interval. Serious adverse events will also be tabulated. The rate of all AEs and SAEs reported in the study will be reported.

All AEs and SAEs will also be summarized by relatedness as described above. Adverse events leading to death or study discontinuation will be provided in listing format.

All device deficiencies will be reported in listing format.

Statistical Analysis Plan		Page 11 of 11
Sponsor	Study	Version
Senseonics	A Post Approval Study to Evaluate the Long-term Safety and Effectiveness of the Eversense® Continuous Glucose Monitoring (CGM) System	1.0

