5.9 Subgroup Analyses

Subgroup analysis of the primary safety, primary effectiveness, and additional safety endpoints will be performed for the following subgroups: sex, age (Age<median , Age≥median), race (Caucasian vs. non-Caucasian), diabetes type (I vs. II), and sensor life (90-day vs. 180-day). In addition, the rate of procedure-related adverse events will be performed for the subgroup defined by subjects receiving care from a healthcare provide with vs. without an MD degree). These analyses are intended to demonstrate consistency of results across subgroups.

Subgroup analyses will be performed using the primary analysis set. For each subgroup, a regression model will be fit that includes a fixed effect for subgroup. If the p-value for the subgroup term is less than 0.15, additional exploratory analysis may be performed to understand any variations in outcomes by subgroup.

For each subgroup analysis, the summary statistics for each subgroup level will be presented.

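### Read literally, SAP 5.2 and protocol 8.1 place secondary and exploratory analyses on the per-protocol set, in conflict with the ITT and primary-set rules of SAP 5.8 and 5.9

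*SAP*

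**What the plan says.** SAP 5.2 and protocol 8.1 define two sets in identical words. The ITT set, all enrolled subjects, is assigned to the primary safety and primary effectiveness analyses. The per-protocol (PP) set is limited to subjects who met the eligibility criteria and who "have demonstrated substantial compliance with the protocol and no significant protocol deviations affecting the primary endpoints". The rule for everything else follows: "Supportive analyses for the primary effectiveness endpoint and all secondary and exploratory analyses will be performed in the PP population".

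The endpoint sections of the SAP add little to this. For the primary safety composite, SAP 5.6.1.1 says: "The endpoint will be evaluated using the ITT analysis set". SAP 5.6.3 (additional safety), 5.6.4 (additional effectiveness) and 5.6.5 (secondary and other) name no set.

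Two later sections do name one. SAP 5.8: "Adverse events (AE) will be reported for the ITT primary analysis population", with a further summary by relatedness. SAP 5.9: "Subgroup analyses will be performed using the primary analysis set", and that section expressly includes the additional safety endpoints.

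**The concern.** This is a post-approval study, meant to describe safety and use in ordinary practice. Several of its descriptive results depend on who is counted: device breakage, related adverse events, procedure success, and serious adverse events by operator experience. A set selected on compliance can look better than the whole cohort if trouble with the device or the procedure goes together with non-compliance or deviations.

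The PP set is also defined by subject. With 1400 planned cycles in 273 inserted subjects, the average is 1400 / 273 = 5.1 cycles each, so excluding one subject removes about five cycles, including any that the deviation did not touch.

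The second problem is practical. If one section sends a rate to PP and another sends the same rate to ITT, two different figures for related adverse events can be reported, and the plan does not say which is the main one.

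**Working it through.** **Step 1. Set by set.** There is no stated figure to reproduce; the check is a cross-reading.

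| Result | Set under SAP 5.2, literal reading | Set named elsewhere in the SAP |
|---|---|---|
| Primary safety composite | ITT | ITT (5.6.1.1), PP as sensitivity analysis (5.6.1.2) |
| Related AEs and related SAEs, overall (5.6.3) | PP, if these count as secondary | ITT, by relatedness (5.8) |
| Device breakage, overall (5.6.3) | PP, if secondary | No rate; device deficiencies are listed (5.8) |
| 5.6.3 endpoints by subgroup | PP, if secondary | Primary set (5.9) |
| HbA1c change, hours of use (5.6.4) | PP, if secondary | Also placed under the primary effectiveness analysis (5.6.2.1), hence ITT |
| Procedure success and SAEs by operator experience (5.6.5) | PP | None |

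**Step 2. Do the 5.6.3 endpoints count as secondary?** The SAP calls them additional. Protocol 8.3, in its paragraph on the other safety endpoints, says: "There are no formal hypotheses or tests for statistical significance associated with secondary endpoints". The protocol therefore uses the word secondary for them. For 5.6.5 no such link is needed, because its title already says secondary.

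**Step 3. The conflict.** The first listed endpoint of 5.6.3, "Rate of all device-related and insertion and removal procedure-related adverse events", is in substance what 5.8 tabulates by relatedness in ITT. SAP 5.6.3 also asks for results overall and by subgroup. (It points to a Section 6.9 that does not exist; the subgroup section is 5.9.) Followed literally, the overall column is PP and the subgroup columns are ITT, so the subgroup counts need not add up to the overall count.

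**Step 4. Scale, on assumptions.** The documents give neither the share of subjects outside PP nor their event rates. Let f be the excluded share, r the subject-level event rate within PP, and k the ratio of the rate in excluded subjects to r.

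- ITT rate = (1 − f)·r + f·k·r = r·[1 + f(k − 1)]
- Relative understatement by PP = 1 − 1 / [1 + f(k − 1)], whatever r is
- Share of subjects with events who are left out = f·k / [1 + f(k − 1)]

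Example with f = 0.20, k = 2, r = 5%: ITT rate = 0.80 × 5% + 0.20 × 10% = 6.0%; PP rate = 5.0%; understatement = 1 − 5.0 / 6.0 = 16.7%; share left out = 0.40 / 1.20 = 33.3%.

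| f | PP subjects of 273 | Understatement, k = 1 / 2 / 3 | Subjects with events left out, k = 1 / 2 / 3 |
|---|---|---|---|
| 10% | 246 | 0% / 9.1% / 16.7% | 10.0% / 18.2% / 25.0% |
| 20% | 218 | 0% / 16.7% / 28.6% | 20.0% / 33.3% / 42.9% |
| 30% | 191 | 0% / 23.1% / 37.5% | 30.0% / 46.2% / 56.3% |

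If k were below 1, the sign would reverse and PP would overstate the rate. For endpoints counted per procedure or per Sensor, f should be the share of procedures or Sensors, not of subjects.

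For an event that is never seen, the one-sided 95% upper bound is 1 − 0.05^(1/n): 1.09% with n = 273, against 1.21%, 1.36% and 1.56% with 246, 218 and 191.

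**Step 5. The denominator under ITT.** ITT is all enrolled subjects: up to 400, of whom 273 are to be inserted. In that case 400 − 273 = 127 subjects never have a Sensor. A subject-level device rate divided by 400 in place of 273 would be 273 / 400 = 0.68 of its value among inserted subjects. A bare move to ITT would therefore exchange one ambiguity for another.

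**The case against.** The strongest reply is grammatical. The opening words about supportive analyses may govern the whole list, so that PP is supportive throughout. That would fit the rest of the SAP: ITT is named as the primary population, PP appears in the endpoint sections only as a sensitivity analysis (5.6.1.2, 5.6.2.2), adverse events are on ITT, and subgroups are on the primary set. On that reading nothing conflicts and nobody is dropped. This is possible, and it may be what was meant. It is not the natural reading, because the sentence speaks of secondary and exploratory analyses rather than endpoints. It would also leave the 5.6.5 endpoints with no main set at all, so the text needs the same correction either way.

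Other parts of the reply stand in full:

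- Related adverse events have an ITT tabulation in 5.8, and breakage has a subgroup analysis in the primary set in 5.9. Some ITT view of both is planned on either reading.
- HbA1c change and hours of use also sit under the primary effectiveness analysis, so they cannot be said to be available in PP only.
- SAP 5.4 requires the number in each set and the reasons for exclusion, so the extent of any selection will be visible.
- The endpoints concerned are descriptive, with no hypothesis test.

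**Conclusion.** The point holds as a conflict between sections and a gap in 5.6.5. It is most direct for procedure success and for serious adverse events by operator experience, which have PP as their only stated set. For the 5.6.3 endpoints it depends on protocol 8.3 calling them secondary. The primary safety test is not affected.

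A reader might infer more, and the documents do not support it:

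- *That the plan removes subjects from safety reporting in general.* It does not. The primary composite and the adverse event tables are on ITT.
- *That the PP results are biased favourably by a known amount.* The direction and size depend wholly on f and k, which the documents do not give. The 9% to 38% range holds only for f of 10% to 30% and k of 2 to 3. At k = 1 the bias is zero, although the excluded subjects' events are still left out.
- *That failed procedures or early removals lead to exclusion.* The deviation criterion covers only those affecting the primary endpoints, and no section makes a difficult procedure a deviation. Protocol 5.4.2 allows an earlier visit when a Sensor stops working.
- *That PP membership will be decided with results in hand.* The timing is not stated. The study is unblinded, so this is an open risk, not a plan.

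**What to change.** 1. Replace the sentence in SAP 5.2 and protocol 8.1 with wording such as: *All primary, additional, secondary, other and exploratory endpoints are analysed in the primary (ITT) set. Analyses in the per-protocol set are supportive only.*
2. Name the set in SAP 5.6.3, 5.6.4 and 5.6.5.
3. For procedure success, breakage and other device or procedure endpoints, state the denominator: all subjects with an attempted insertion, or all attempted procedures or Sensors, as suits the endpoint.

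The cost is one sentence in each document and a line in each of three SAP sections. No new data, visits or sample size are involved. SAP section 6 already provides for an amended SAP before the analysis, so the clarification can be made there while the protocol wording is brought into line.
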